4.4.1. G4 and ECG Synchronization

The minutes and hour display on the G4 and the ECG clocks must be synchronized to within 1 second of variation prior to the start of PICC insertion data collection. This synchronization must be performed prior to each subject use.

4.4.2. PICC Placement Using G4

Standard PICC placement and G4 operating procedures will be followed according to institutional policy. The G4 data will be de-identified by replacing the MRN number with the subject ID number before transferring the data to the sponsor. The catheter selected, the final length inserted, exposed length of catheter, and location of lead placement for both devices will be recorded. Anatomical location of access site, including arm and vessel used for PICC insertion as well as the procedure start and stop time will also be documented. The data for each subject will be submitted to the sponsor.

4.4.3. Chest X-Ray: Image Capture and Radiology Review

PICC tip location in the lower one third of the superior vena cava/cavo-atrial junction will be documented by radiograph. Any patient items that may interfere with visualization, including jewelry, and ECG patches/wires, should be removed prior to capturing the image. Replace ECG patches/wires prior to the start of the data collection period. The image acquired should keep the arm with the PICC at the same angle from the patient's midline as performed during PICC insertion. Provide support for the arm during the X-ray procedure. X-ray beam should be 90° perpendicular to the film. Verify angle. The distance between the beam and the film should be maintained at 48 inches. Measure this to ensure that it is correct. X-ray should be shot at end-expiration during normal breathing. Do not

ask the patient to take a deep breath as this will move the PICC line and will not provide a proper assessment of the catheter tip.

ECG and G4 recording should be terminated before the x-ray. A de-identified copy of the x-ray image will be transferred to the study sponsor.

A designated radiologist will be selected to review and provide interpretation for all radiographs for this study to ensure consistency. The radiologist interpretation will be submitted to the sponsor.

4.4.4. Demographic and Procedural Data Collection

- The following demographic data will be collected: gender, age (in years), height in cm, weight in kg, and race/ethnicity will be collected.
- The following medical information will be collected: present diagnosis requiring PICC placement and cardiovascular disease history, including pacemaker, and/or a history of arrhythmic heart conditions such as: Atrial fibrillation, atrial flutter, severe tachycardia, or pacemaker driver rhythms will be captured for all subjects enrolled.
- The following procedural data will be collected: anatomic location of the access site (right/left arm and vein), catheter selected (number of lumens, length, and manufacturer), PICC insertion procedure start and stop times, lead placement (G4 and ECG machine), and final catheter length inserted and exposed.

4.5. Adverse Events (AE) Assessment

Adverse events will be assessed, documented, and reported to the Sponsor as outlined in Section 5.

4.6. End of Study Status: Subjects will be categorized based upon their end of study status as described below.

4.6.1. Completed Study

Subject is considered to have completed the study after completion of all study procedures.

4.6.2. Subject Initiated Early Termination from Study:

A subject's participation in the study will be immediately terminated upon subject withdrawal of consent. Upon termination a final AE assessment should be performed by the study staff.

4.6.3. Investigator Initiated Early Termination from Study:

If the Investigator feels that the subject can no longer fully comply with the requirements of the study, if any of the study procedures would not be in the best interest of the subject, or if any of the study procedures cannot be completed on the subject (data collection on 12-lead

ECG and/or chest x-ray) the investigator should withdraw the subject from the study. Upon termination a final AE assessment should be performed by the study staff.

5. Assessment of Safety

5.1. General

The safety of the subjects will be prioritized for this clinical study. Each participating Investigator has the responsibility for the safety of the subjects under their care. Since the only study procedures are the use of ECG during the PICC insertion and the chest x-ray post-insertion, only AEs related to the study procedures will be reported in the case report form (CRF) as described below. Incidences of device malfunction and adverse events related to the PICC device and G4 system should be reported to Teleflex in accordance with institutional policy and procedure and regulatory requirements.

5.2. Adverse Events

An adverse event (AE) is any unfavorable medical occurrence affecting a clinical investigation Subject, which does not necessarily have a causal relationship with the treatment or procedure. An AE can therefore be any unfavorable and unintended sign, symptom, or diagnosis associated with the use of the study device, whether or not it is considered related to the device. Adverse events should be reported in accordance with International Conference on Harmonization (ICH) guidelines.

For all adverse events, the investigator must pursue and obtain information adequate to determine the severity, causality (e.g., study procedure or other cause), and outcome of the event and to assess whether it meets the criteria for classification as a serious adverse event. Follow-up of the event is required until the event or its sequelae resolve or stabilize at a level acceptable to the investigator and the study sponsor/monitor. Adverse event evaluation will begin from the start of data collection through completion of the chest x-ray. Adverse events reported to the investigator subsequent to the subject's participation will also be evaluated.

5.2.1. Relationship to Study Device/ Procedure

Adverse events will be assessed for relationship to the study procedures and categorized as follows:

Not Related

Possibly Related

Definitely Related

5.2.2. Unanticipated Adverse Device Effect

An unanticipated adverse device effect (UADE) is a serious adverse effect that is possibly caused by or related to a study device or procedure not previously identified in nature, severity or degree, or any other unanticipated serious problem associated with a device. UADEs associated with use of the 12-lead ECG should be reported to the sponsor on the eCRF and to the ECG manufacturer in accordance with institutional policy and procedure and regulatory requirements.

5.2.3. Non-serious Adverse Events

Non-serious adverse events determined by the principal investigator (PI) to have at least a possible relationship to the 12-lead ECG use, or the chest x-ray study procedures will be reported to the sponsor on the eCRF.

5.2.4. Serious Adverse Events (SAE)

A serious adverse event is any adverse event that:

- Results in death
- Is life-threatening: A life-threatening adverse event is defined as any adverse experience that places the subject at immediate risk of death from the reaction as it occurred.
- Results in inpatient hospitalization or prolongation of existing hospitalization: Hospitalization is defined as any inpatient or outpatient/short-stay admission as a result of a precipitating, device or treatment-related emergent adverse event. For chronic or long-term patients, inpatient admission also includes transfer within the hospital to an intensive care inpatient unit.
 - Hospitalization for administrative reasons or a non-worsening pre-existing condition should not be considered adverse events (e.g., admission for workup of a persistent pretreatment lab abnormality, yearly physical exam, protocol-specified admission, elective surgery). Preplanned treatments or surgical procedures should be noted in the baseline documentation. However, if a hospitalization due to an unknown event occurs, it should be considered as a serious adverse event.
 - Prolongation of hospitalization is defined as any extension of an inpatient hospitalization beyond the stay anticipated/required for the original reason for admission, as determined by the investigator or treating physician.
- Results in persistent or significant disability/incapacity: Disability is a substantial disruption of a person's ability to conduct normal activities of daily living.
- An adverse event that is not fatal, life-threatening, or requires hospitalization may be considered medically significant and therefore serious when, in the opinion of the investigator, it could jeopardize the subject and may require medical or surgical intervention to prevent any of the above outcomes.

5.2.5. SAE Reporting

Serious adverse events must be reported to the sponsor immediately, within 24 hours of knowledge of the event, if it occurs or comes to the attention of the investigator any time a subject is on study or reported to the investigator subsequent to the subject's participation. SAEs may be reported by emailing the SAE documents to:

Teleflex Incorporated
Global Clinical Operations
Email: [contact]

An SAE report form and relevant documentation (if any) should be submitted electronically to Teleflex and to the IRB, in accordance with IRB reporting requirements. The initial report should include at minimum the following information:

- Subject ID number, sex, age
- Study device/procedure suspected relationship to the SAE

- SAE term and date of event

Follow-up information including causality, severity, outcome, action taken, and concomitant medications should be communicated to the sponsor as soon as possible.

6. Potential Risks and Benefits

For the purpose of this study, subjects will have continuous 12-lead ECG tracings performed during PICC insertion and one chest x-ray of the inserted catheter at the end of the procedure. The chest x-ray and 12-lead ECG are not part of the routine PICC insertion procedures. These risks are outlined further but are considered to be minimal risk procedures. There is no perceived clinical benefit to subjects from participation in this study.

There are standard risks of participating in a research study, for example given the potential of accidental disclosure of subject's confidential information. Every effort will be made to ensure that subject personal information remains confidential at all times, including application of Subject ID and redacting personally identifying information before submitting to the Sponsor.

Since subjects participating in the study will be receiving PICC insertion per standard of care, and the G4 is within the standard procedures for use during PICC device placement at this institution, these are not considered study procedures. Consent for PICC placement will be obtained as part of the standard of care and will not be associated with this study.

The internal G4 device records ECG data during the central catheter line insertion that is used to detect correct placement. This ECG recording will be de-identified of the subject PHI and replaced with subject number prior to being sent to Teleflex.

Risks associated with 12-lead ECG:

The risks associated with use of the ECG machine include:

Minor discomfort during electrode removal

Skin irritation, itching, rash or redness from the ECG electrode pads.

Hair that may prevent an adequate tracing will be removed via shaving, pending the subject approval.

No PHI will be inputted into the ECG machine (only subject number) to maintain subject confidentiality.

Risks associated with photographic images:

A thoracic photograph will be taken to document the placement of the ECG leads. The risk associated with the photographic images is the risk of loss of privacy. Pictures of the body above the shoulder i.e., the face will not be included in the photographic images. Stored images will not contain PHI (only subject number) to maintain subject confidentiality.

Risks associated with chest x-rays:

Radiation exposure from the x-rays needed for this study is about the same as the average person receives from normal radiation sources, such as sunlight and TV during a 10-day period. There is a slight chance of cancer from excessive exposure to radiation from x-rays.

Minimization of risk

There are no significant risks associated with the study related procedures of this clinical protocol.

7. Statistical Consideration

7.1. Sample Size Justification

The sample size is not intended to be statistically justified. Data will be collected from 20 evaluable subjects and analyzed to support the determination of feasibility of this synchronized data for the algorithm refinement process.

7.2. Study Populations for Analysis

7.2.1. Safety Analysis Population (Intent to Treat/ITT)

All subjects on whom the G4/ECG data collection procedure was started shall be included in the assessment of safety (ITT population). Subjects who withdraw or are withdrawn from the study prior to study completion will be included through the point that they exited the study. All available data will be included in the analysis.

7.2.2. Feasibility Analysis Population

Non-evaluable subjects will be excluded from the feasibility analysis population. See Section 3.2 - Sample Size for definition of evaluable subject.

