	Product: Teleflex Arrow Vascular Positioning System G4
	Development Phase: Post Market
Title: Vascular Positioning System G4 Algorithm ECG Data Collection for Model Training Study, A Single Center Prospective Clinical Study	
Investigators: [name] [name], RN Duke University Hospital	Sponsor Management: Teleflex Incorporated Study Management: [name] PhD, Clinical Trial Manager Study Monitor: [name], Clinical Research Associate
Study Design: Prospective Clinical Study	
Objective: The objective of this study is to collect and analyze intravascular and extravascular echocardiogram (ECG) data from subjects receiving peripherally inserted central catheters (PICC) while using the Vascular Positioning System G4 and a 12 lead ECG machine. The data obtained will be used to evaluate the correlation between intra- and extravascular ECG data and determine usability in updating the G4 algorithm.	
Primary endpoint: The primary endpoint is synchronized digital data collected from the G4 and ECG machines during the PICC insertion procedure, including a photographic image documenting ECG lead placement, and a chest x-ray (post procedure).	
Number of Subjects:30	Number of Study Centers: 1
Duration of Evaluation: Time required for PICC insertion	Estimated Duration of Study: 4 months

Contents

1. Introduction	5
2. Objective of Study and Study Design	6
3. Selection of Subjects.....	6
4. Study Procedures.....	7
5. Assessment of Safety	11
6. Potential Risks and Benefits.....	13
7. Statistical Consideration	14
8. Quality Control and Quality Assurance	14
9. Study Monitoring	15
10. Institutional Review Board Review.....	15
11. Data Handling and Recording.....	16
12. Confidentiality	17
13. Publication Policy.....	17
References	18

1. Introduction

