2.1. Primary Objective

The objective of this study is to collect and analyze synchronized intra- and extravascular ECG data from subjects receiving PICC insertion while using the G4 and a 12-lead ECG machine. The data will be analyzed to evaluate the correlation between intra- and extravascular ECG data.

Primary Endpoint

The primary endpoint is the successful collection of the following data: synchronized digital data collected from the G4 and ECG machines during the PICC insertion procedure, photographic images documenting ECG lead placement, and a chest x-ray of the inserted PICC (post procedure). A copy of the data will be submitted to the sponsor.

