3.2. Sample Size

A sample size of up to 30 adult subjects will be enrolled to obtain 20 evaluable subjects. Including a maximum of 10 subjects in whom the G4 system was used for tip navigation but the blue bull's eye was not achieved and 10 subjects where the blue bull's eye served as confirmation for tip placement. An adult subject per The Federal Food, Drug, and Cosmetic Act (FD&C Act) is persons 22 years of age and older at the time of treatment.^{vi} To be considered an evaluable subject, data must be collected for the duration of the PICC insertion procedure on both the G4 and the ECG machines, the post-insertion chest x-ray completed, and photographic documentation of the ECG lead placement captured. Non-evaluable subjects will be replaced to meet the target sample size.

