4.4. PICC Insertion, ECG, Chest X-ray, and Data Collection

The ECG recording and chest x-ray will be performed as described in the sections below. The ECG machine should start recording data prior to the first skin puncture and continue recording through catheter tip placement.

The study staff will defer to the institution's policy for confirming proper tip placement.

After successful PICC tip placement , ECG data collection can be terminated. Up to a maximum of 10 subjects in whom the blue bull's eye was not achieved during PICC navigation will be included as evaluable subjects. Beyond, these 10 subjects, **if the blue bull's eye is not achieved the subject's participation in the study will be terminated and no additional study procedures will be performed.** If an ECG lead should fall off during the data collection period, the lead can be replaced, as long as, the G4 system is not displaying the orange caution indicator on the screen. If the caution indicator is displayed refrain from replacing the lead. If the ECG stops recording during the data collection period, it will not be resumed.

Data Collection Procedures

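### Section 7 plans no summary of the primary endpoint (successful data collection), the evaluable set cannot supply one, and the photograph rule that helps define that set contradicts other sections

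*Combined protocol and SAP*

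**What the plan says.** Section 2.1 states: "The primary endpoint is the successful collection of the following data: synchronized digital data collected from the G4 and ECG machines", and goes on to add lead-placement photographs and a post-procedure chest x-ray. The synopsis lists the same items without the word for success: "The primary endpoint is synchronized digital data collected from the G4 and ECG machines during the PICC insertion procedure".

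Section 3.2 defines an evaluable subject in two parts: "data must be collected for the duration of the PICC insertion procedure on both the G4 and the ECG machines", and "the post-insertion chest x-ray completed, and photographic documentation of the ECG lead placement captured". It sets the numbers, "A sample size of up to 30 adult subjects will be enrolled to obtain 20 evaluable subjects", and the replacement rule, "Non-evaluable subjects will be replaced to meet the target sample size".

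Section 7.2 names two populations. The one in 7.2.1 holds everyone in whom G4/ECG collection was started and is assigned to the assessment of safety. For the one in 7.2.2: "Non-evaluable subjects will be excluded from the feasibility analysis population". Section 7.3 is a single sentence about the feasibility of refining the algorithm.

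The protocol foresees incomplete collection. Section 4.4 says: "If the ECG stops recording during the data collection period, it will not be resumed". Section 4.6.3 has the investigator withdraw a subject in whom the ECG or x-ray cannot be completed.

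On photographs the sections differ. Section 2.2 promises them for all enrolled subjects, and 3.3 and 3.4 make willingness to be photographed an eligibility condition for everyone. Section 3.1 restricts images to men, and 4.3 and 4.3.1 restrict them to some consenting men. Section 3.1 also opens by describing a male population and then says that both sexes will be recruited.

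**The concern.** When the primary endpoint is whether the data were successfully collected, its natural result is how many subjects it was achieved in, out of how many attempted, and why it failed in the others. Section 7 asks for none of this. The population that carries the feasibility label admits only subjects in whom collection succeeded, apart from clock synchronization. A stopped ECG recorder, a missed x-ray or a missing photograph is a failure of the 2.1 endpoint, but it would not be visible there, and the subject would be replaced. The study report could follow the plan exactly and still not say how often collection failed.

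The photograph rule decides who counts as a failure, so it has to be settled before any such count means anything. As written, a subject can be non-evaluable only because the protocol never intended to photograph that person.

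**Working it through.** **Step 1. Compare the endpoint with the evaluable definition.**

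| Component | Endpoint (2.1) | Evaluable (3.2) | Planned in whom |
|---|---|---|---|
| G4 recording | yes | yes, whole procedure | all |
| ECG recording | yes | yes, whole procedure | all |
| Clock synchronization | yes (the data are to be synchronized) | not named | each subject, to within 1 second (4.4.1) |
| Chest x-ray | yes | yes | all enrolled (2.2), but not those stopped under the bull's-eye cap (4.4) |
| Photographs | yes | yes | all enrolled (2.2); men (3.1); some consenting men (4.3, 4.3.1) |

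Four of the five components are conditions of entry to the 7.2.2 population. For those four, a collection rate computed in that population is x/x = 100% whatever happens in the study. Only synchronization could vary.

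**Step 2. Look for the endpoint in Section 7.** Section 7.1 refers to 20 evaluable subjects and feasibility for algorithm refinement. Section 7.2.1 concerns safety, 7.2.2 the evaluable set and 7.3 the algorithm. None gives a count, proportion, denominator or interval for the 2.1 endpoint.

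**Step 3. The plan's own figures.** The inputs are 20 evaluable and a cap of 30 enrolled (3.2). Section 7.1 says the size is not statistically justified, and no attrition rate is given, so there is no derivation to reproduce. As arithmetic, 20/30 = 0.667 and 20/(1 − 1/3) = 30. The two numbers are therefore compatible with up to one third of enrolled subjects being non-evaluable. That third is back-calculated; the documents do not state it.

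**Step 4. Illustrate what the denominator does.** Take x = 20 complete subjects and an assumed denominator n. The exact (Clopper-Pearson) 95% limits are the 0.025 quantile of Beta(x, n − x + 1) and the 0.975 quantile of Beta(x + 1, n − x); when x = n the upper limit is 1.

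| x/n | Proportion | Exact 95% CI |
|---|---|---|
| 20/20 (evaluable set) | 100% | 83 to 100, nominal only |
| 20/22 | 91% | 71 to 99 |
| 20/25 | 80% | 59 to 93 |
| 20/28 | 71% | 51 to 87 |
| 20/30 | 67% | 47 to 83 |

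Using only started subjects can also hide failures. If 28 are enrolled and 3 fail before recording begins (both assumed), the result is 20/25 = 80% of started but 20/28 = 71% of enrolled.

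**Step 5. The photograph rule read literally.** Let p be the share of enrolled subjects who are photographed men. At most 30p can be evaluable, so 20 evaluable needs p ≥ 20/30 = 67%, with exactly 67% sufficing only if all of them are complete on everything else. For assumed p of 40%, 50%, 60% and 75%, the ceilings are 12, 15, 18 and 22 (22.5 rounded down).

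**The case against.** The strongest reply is that feasibility here means usability of the data for refining the algorithm (1.2, 7.1, 7.3), and complete records are the right set for that. This stands. A reader might infer that the 7.2.2 exclusion is itself an error; the documents do not support that. The gap is in 7.3, which gives the 2.1 endpoint no analysis.

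A reader might also infer that the sponsor plans to report 100% success, or that a third of subjects will fail. Neither is supported. No section proposes a collection rate in the evaluable set. Thirty is a cap, and some attrition may be administrative, since subjects without a bull's-eye beyond the permitted 10 are stopped under 4.4.

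Section 7.2.1 carries an intent-to-treat label, keeps withdrawn subjects up to exit, and says that all available data enter the analysis. This is the best counter-evidence, but the population is tied to safety and no endpoint analysis is attached to it. It also misses enrolled subjects in whom collection never starts. Elsewhere, 9.2 covers deviations, 10.4 requires a closure report with an outcome summary, and 11.5 lists insufficiently complete data as a reason to stop the study. Completeness is not ignored, but none of these sections specifies a collection count.

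It might be thought that the counts can always be recovered from the site's records. Section 4.2 requires the log to give reasons for screening failure only, and 4.6 provides three end-of-study statuses. Neither is stated to record which component was missing or why.

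Finally, a single-centre study with no threshold needs no inferential apparatus. This is fair: plain counts with reasons are the essential part, and intervals are optional.

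**Conclusion.** The concern holds as two linked points. First, the primary endpoint of 2.1 has no planned summary, and the only non-safety population cannot serve for one, although it is suitable for the correlation and algorithm analyses. Second, the evaluable definition in 3.2 conflicts with the sections that limit photographs. Read literally, it makes every woman and every unphotographed man non-evaluable and replaceable, and at least 67% of enrolled subjects must then be photographed men with complete data if 20 are to be reached under the cap.

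The size of any unreported failure is unknown, because the documents give neither the number enrolled nor the number started. The percentages in Step 4 rest on assumed denominators and on 20 complete subjects, and illustrate the possible range only. No success threshold depends on the rate and no safety issue arises. This is a reporting gap and a definitional contradiction that should be considered for correction.

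**What to change.** 1. Reconcile the photograph requirement across the synopsis, 2.1, 2.2, 3.1 (including its opening male-only description), 3.2, 3.3, 3.4, 4.3, 4.3.1 and Section 6. A subject for whom no photograph is planned should not be non-evaluable for that reason alone. Record before the procedure whether photographs are planned, so that a missed photograph cannot be reclassified afterwards.
2. State in 7.3 that the 2.1 endpoint is reported descriptively, as counts and proportions (exact 95% CI optional), overall and by component: G4 recording, ECG recording, clock synchronization, x-ray, and photograph where planned. Report it among all enrolled subjects and among those in whom G4/ECG collection was started, with reasons for failure. Show subjects stopped under the bull's-eye cap separately, as administrative.
3. Keep the 7.2.2 evaluable set for the correlation and algorithm analyses.

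The cost is a few sentences in Section 7, a consistent photograph rule in the places listed, one table, and case report form items for whether photographs were planned and for completion of each component with the reason if missing. No extra subjects or procedures are needed. The reported collection rate may look less favourable.
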